University of Research Integrity and Compliance Office

Protocol Title: Mechanisms of Adaptation to Exercise in Health & COPD:
Oxidative stress links aging, activity and mobility

Protocol: # IRB_00032404

Approval date: 10/30/17

PI: [name]., D.Sc.

METHODS

Subjects and General Procedures. 42 young (25 ± 1 yrs) and 45 older (71 ± 1 yrs) healthy volunteers participated in the current study. All subjects were non-smokers, normotensive ($<140/90$ mmHg), and free of overt cardiovascular disease as determined by health history questionnaire and physical examination. Exclusion criteria included subjects with diagnosed cardiovascular disease, diabetes, hypercholesterolemia, hypertension, and women who were pregnant. Subjects were not taking any prescription medication, and were asked to abstain from vitamin supplements for 10 days prior to enrollment and during the course of the study. Subjects arrived to the laboratory at 0800 in a fasted state, having abstained from exercise and caffeine for 12 hours prior, in accordance with recently published guidelines ²⁴. Premenopausal females were studied within the first five days of their menstrual cycle, as FMD measurements of the brachial artery have been documented to fluctuate with menstrual phase. Protocol approval and written informed consent were obtained according to the University of Utah and Veteran Affairs Institutional Review Board requirements. All data collection took place with subjects supine, in a thermoneutral environment.

Antioxidant Supplementation. All subjects reported to the laboratory twice within one week (>48 hrs apart) and received the antioxidant (AO) cocktail or placebo (PL) in a balanced, double-blind, crossover design. Supplements were taken in two doses, separated by 30 minutes to improve absorption, consumed 90 and 60 minutes prior to the FMD protocol. The first dose consisted of 300 mg of alpha-lipoic acid, 500 mg Vitamin C, and 200 I.U. Vitamin E, and the second dose was 300 mg alpha-lipoic acid, 500 mg Vitamin C, and 400 I.U. Vitamin E. Placebo microcrystalline cellulose capsules of similar taste, color, and appearance were likewise

consumed in two doses within the same time frame. We have previously reported the efficacy of this antioxidant cocktail to reduce carbon- and O₂-centered free radical levels, as measured by electron paramagnetic resonance (EPR) spectroscopy, in both young ²⁵ and older ²⁶ subject populations.

Measurements. Details of the FMD procedure have been described previously ²⁷, and were performed in accordance with current recommendations ²⁴. Briefly, a blood pressure cuff was placed on the right arm proximal to the elbow and distal to the placement of the ultrasound Doppler probe on the brachial artery (BA). The BA was insonated approximately midway between the antecubital and axillary regions, and measurements of BA diameter and blood velocity (V_{mean}) measurements were obtained continuously at rest and for 2 minutes following cuff deflation (Logiq 7, GE Medical Systems, Milwaukee, WI).

Analyses. V_{mean} was automatically calculated using commercially available software (Logiq 7). End-diastolic, ECG R-wave gated images were collected via video output from the Logiq 7 for off-line analysis of BA vasodilation using automated edge-detection software (Medical Imaging Applications, Coralville, Iowa). Flow-mediated vasodilation (FMD) was quantified as the maximal percent change in BA diameter following cuff release. Shear rate was calculated as:

Shear Rate (s⁻¹) = V_{mean} • 8 / vessel diameter. Blood flow was calculated as: *Blood flow (ml • min) = (V_{mean} • π • [Vessel Diameter/2]² • 60).* For both shear rate and blood flow, cumulative area-under-curve (AUC) values were integrated with the trapezoidal rule and calculated as $\sum \{y_i[x_{(i+1)} - x_i] + (1/2)[y_{(i+1)} - y_i][x_{(i+1)} - x_i]\}$. Reactive hyperemia was quantified as cumulative BA blood

flow for two minutes (AUC) following cuff occlusion. Normalized FMD was calculated by dividing FMD (%) by the cumulative shear rate AUC at the time of peak BA vasodilation.

Assays. In a subset of subjects ($n = 18$ young, $n = 30$ older), blood samples were obtained from the antecubital vein immediately prior to FMD testing on both PL and AO visits. Total AO capacity was assessed by the ferric reducing ability of plasma (FRAP) assay, and endogenous AO activity was assessed by determining superoxide dismutase (SOD, Cayman Chemical Company, Ann Arbor, MI). Plasma ascorbate concentration was also determined (Cosmo Bio, Carlsbad, CA). Quantitative determination of thiobarbituric acid reactive substances (TBARS) was performed to assess lipid peroxidation, a marker of oxidative stress (Bioassay Systems, Hayward, CA). Total nitrate and nitrite were measured using a standard colorimetric nitrate reductase/Greiss reaction assay (Cayman Chemical, Ann Arbor, MI). Measurement of nitrotyrosine (3-NT) was performed using competitive ELISA (Cell Biolabs, San Diego, CA). A lipid panel was obtained for all subjects by standard techniques.

Statistics. Statistics were performed with the use of commercially available software (SigmaPlot 11, Systat Software Inc., Point Richmond, California, USA). Repeated measures two-way analysis of variance (ANOVA) was used to identify significant changes in measured variables between conditions and groups, with the Bonferroni test used for post-hoc analysis when a significant main effect was found. All group data are expressed as mean \pm standard error. Significance was established at $P < 0.05$.

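### The two-visit crossover is analysed without a period term, so any visit effect costs power for the antioxidant effect and its interaction with age, and could bias the interaction if visit order was uneven within age groups

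*Combined protocol and SAP*

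**What the plan says.** The Antioxidant Supplementation paragraph has a two-visit design. "All subjects reported to the laboratory twice within one week", more than 48 hours apart, and "received the antioxidant (AO) cocktail or placebo (PL) in a balanced, double-blind, crossover design". It does not say whether the balance holds within the young and within the older group or only overall, and it gives no count of subjects per order.

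The sample is stated under Subjects and General Procedures: "42 young (25 ± 1 yrs) and 45 older (71 ± 1 yrs) healthy volunteers participated in the current study".

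The Statistics paragraph names the two factors of the only model: "Repeated measures two-way analysis of variance (ANOVA) was used to identify significant changes in measured variables between conditions and groups". Bonferroni post-hoc tests follow a significant main effect, and the threshold is 0.05. No visit, period, order or sequence term appears anywhere in the document.

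For the assays, a subset of 18 young and 30 older subjects was used, and "blood samples were obtained from the antecubital vein immediately prior to FMD testing on both PL and AO visits". The order split in that subset is not given.

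**The concern.** In a two-visit crossover, a systematic difference between visit 1 and visit 2 enters each subject's AO minus PL difference. It enters with a plus sign if AO came second and a minus sign if AO came first. Balancing the order cancels this in the average, but it does not take it out of the spread. A model with condition and group only therefore counts the visit effect as random error.

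Two consequences follow if a visit effect exists:

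- **Order even within each age group.** The estimates are essentially unbiased, but the error variance is too large. The AO and AO by age tests lose power and become conservative.
- **Order balanced only overall.** The AO main effect stays nearly unbiased. The AO by age interaction, which compares the AO response of young and older subjects, is shifted in proportion to the difference between the groups' order splits.

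A reader cannot tell from the document which of these two cases applies.

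**Working it through.** **Inputs from the document.** 42 young and 45 older subjects (87 in all), two visits, alpha 0.05, model with condition and group. Assay subset: 18 young, 30 older. There is no power or sample-size figure to reproduce.

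**Assumptions.** Everything is expressed in SDd, the standard deviation of AO minus PL apart from any visit effect. Assumed effects are 0.6 SDd for AO by age and 0.3 SDd for AO. The shift (visit 2 minus visit 1) is varied from 0.1 to 0.7 SDd. If visit errors are equal and independent, SDd = √2 × within-subject SD, so 0.5 SDd is about 0.7 within-subject SD.

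**Model.** For each subject, d = effect + shift × o + e, with o = +1 if AO was at visit 2, o = −1 if at visit 1, and SD(e) = 1. The condition by group F test equals the square of the two-sample t test on d, with 85 error degrees of freedom. Without a shift, the standard error of AO by age is √(1/42 + 1/45) = 0.215.

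**A. Order even within groups (21/21 young; 22/23 or 23/22 older).** Omitting order raises the error variance to about 1 + shift², so the estimated standard error grows by √(1 + shift²). The actual sampling spread of the estimate does not grow, because the split is fixed. That is why the test becomes conservative.

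Worked case, shift 0.5, AO by age:
- estimated standard error = 0.215 × √1.25 = 0.215 × 1.118 = 0.240
- difference needed for significance = 1.988 × 0.240 = 0.477 (1.988 is the t quantile on 85 df)
- residual bias from the odd 45th subject = ± 0.5/45 = ± 0.011
- power ≈ Φ[(0.6 ± 0.011 − 0.477)/0.215] = Φ(0.52) to Φ(0.62), or 70% to 73%
- with no shift: Φ[(0.6 − 1.988 × 0.215)/0.215] ≈ Φ(0.80) = 79%

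Simulation (100,000 trials per cell) gives, for AO and AO by age alike:

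| Shift (SDd) | Estimated SE | Power, no period term | Power, with period and group × period | Type I error, no period term |
|---|---|---|---|---|
| 0.1 | +0.5% | 78–79% | 79% | 4.8–4.9% |
| 0.2 | +2% | 77–78% | 79% | 4.5–4.6% |
| 0.3 | +4% | 75–78% | 79% | 4.0–4.1% |
| 0.5 | +12% | 70–73% | 79% | 2.8–2.9% |
| 0.7 | +22% | 61–67% | 79% | 1.6–1.7% |

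**B. Order balanced only overall (43/44).** The bias in AO by age is shift × (mean o in young − mean o in older). Splits are AO second : AO first.

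| Young | Older | Bias factor | AO by age type I error at shift 0.5 |
|---|---|---|---|
| 23:19 | 20:25 | 4/42 + 5/45 = 0.206 | 4.8% |
| 24:18 | 19:26 | 6/42 + 7/45 = 0.298 | 6.9% |
| 25:17 | 18:27 | 8/42 + 9/45 = 0.390 | 10.0% |

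In the last row the bias is 0.390 × 0.5 = 0.195 SDd. Across shifts 0.1, 0.2, 0.3, 0.5 and 0.7, that row gives 5.3%, 6.0%, 7.2%, 10.0% and 13.1%. With period and group by period in the model, type I error is 4.8–5.1% throughout.

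If order was assigned without regard to age, the hypergeometric distribution (42 young from 87, with 43 or 44 in one order) gives a probability of 0.286 for a young split of 24:18 or worse, and 0.135 for 25:17 or worse. Averaged over all such draws, AO by age type I error is 5.0%. Inflation arises only given an uneven realised split.

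**C. Assay subset.** If the subset was a random choice from balanced groups, expected bias is about zero and type I error at shift 0.5 is 3.8–4.1%. Splits of 11:7 and 17:13 leaning the same way would give 5.7% for AO. Splits that uneven or worse in the same direction have probability 0.062.

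**The case against.** The strongest reply is that no visit effect has been shown and the visits were closely standardised: same hour, fasted, no exercise or caffeine for 12 hours, supine, thermoneutral, double-blind, both within a week, with automated edge detection. A shift of 0.5 SDd between two such visits would be large. The document does say that FMD varies with menstrual phase, and cycle day advances between visits, but testing is confined to the first five days of the cycle.

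Next, with even order the omission makes the test conservative, so it cannot manufacture a positive finding. The power loss also depends on baseline power being near 80%; at an AO by age effect of 0.9 SDd and a 0.5 shift, power is about 97–98% against 99%. Finally, balanced may well mean balanced within each age group, and nothing in the document suggests otherwise.

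Most of this stands, and it is why the point is minor. The inflated error rates in B and C are conditional illustrations, not evidence of a likely error. What does not fall away is that standardising visits reduces a visit effect without measuring it, and that balance protects against bias but not against lost precision. Uneven order is also necessary but not sufficient for bias in AO by age. If both groups leaned the same way (25:17 and 27:18) with a common visit effect, the interaction would be almost unbiased and the AO main effect would carry the bias instead (0.098 SDd and 10.0% type I error at shift 0.5). That would need overall imbalance, contrary to the stated design.

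**Conclusion.** The concern holds, as a minor point. The design controls visit order and the analysis does not use it. If order was even within age groups, the loss is slight up to a shift of 0.3 SDd (75–78% power against 79%) and material from about 0.5 SDd (70–73%), with no added false positives. If order was balanced only overall, AO by age could be biased by 0.21 to 0.39 times the shift at the splits examined, but there is no inflation on average over random allocations. All of this rests on assumed effects and an assumed visit effect, because the document supplies neither. For the assay subset the point is a reason to report the split, not a demonstrated bias.

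**What to change.** Fit a linear mixed model with random subject and fixed group, condition, group by condition, period and group by period. Equivalently, analyse each subject's AO minus PL difference by visit order, age group and their interaction. Report the period-adjusted AO and AO by age estimates for FMD and for the assays, and the order split by age group in the full sample and in the subset. Group by period is worth including: with splits of 25:17 and 27:18 and a visit effect that differs by age, a common period term left a bias of 0.097 SDd in AO by age, which the added term removed.

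The cost is 1–2 degrees of freedom and a line of text. With no visit effect, AO by age power is 79% with or without the terms if order is even within groups. At 25:17 and 18:27 it is 77.4% with them against 79% without (variance up 4%). No new data should be needed, since visit order must be known to label each visit AO or PL; this is inferred, as the document does not say so. The change does not address carryover.

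### Single-step Bonferroni for the post-hoc comparisons is valid but needlessly conservative: Holm's step-down version never rejects less at the same family-wise error, with a gain that may be zero

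*Combined protocol and SAP*

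**What the plan says.** All of this is in the combined protocol and SAP, under METHODS.

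- **Design** (Antioxidant Supplementation): subjects "received the antioxidant (AO) cocktail or placebo (PL) in a balanced, double-blind, crossover design". With two age groups, this gives two conditions within subject by two groups between subjects, or four cell means.
- **Size** (Subjects and General Procedures): "42 young (25 ± 1 yrs) and 45 older (71 ± 1 yrs) healthy volunteers participated in the current study". Under Assays, blood was taken in a subset of 18 young and 30 older.
- **Adjustment** (Statistics): the rule for follow-up tests reads "with the Bonferroni test used for post-hoc analysis when a significant main effect was found". The significance level is 0.05.
- **Main analysis** (same paragraph): the model that these follow-up tests depend on is given as "Repeated measures two-way analysis of variance (ANOVA) was used to identify significant changes in measured variables between conditions and groups".

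The documents do not say how many comparisons form a post-hoc family, which comparison or outcome is primary, or what effect size, SD, within-subject correlation or power was assumed. They do not state sidedness or mention a stepwise procedure.

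**The concern.** Single-step Bonferroni tests every one of m comparisons at 0.05/m. Error control requires that only of the smallest P value. Once one hypothesis has been rejected, at most m − 1 true null hypotheses can remain, so the next P value can be tested at 0.05/(m − 1), and so on. Keeping the strictest threshold throughout gives up power and buys no lower family-wise error limit.

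At stake are the follow-up comparisons of cell means: antioxidant against placebo within each age group, and young against older on each visit. If two or more real differences exist, as when an age gap accompanies an antioxidant effect in older subjects, Bonferroni can miss the second although Holm would find it in the same data at the same 5% limit.

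**Working it through.** **1. No planned figure to reproduce.** The documents contain no power or sample-size calculation.

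**2. Dominance, which needs no trial inputs.** Order the P values p(1) ≤ … ≤ p(m). Holm compares p(j) with 0.05/(m − j + 1) and stops at the first failure.

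- *Never fewer rejections.* Every Holm threshold is at least 0.05/m. If a P value is at or below 0.05/m, so are all smaller ones; each passes its step and Holm reaches and rejects it.
- *Same error limit.* With m₀ true nulls, the first of them to be tested comes no later than step m − m₀ + 1, where the threshold is at most 0.05/m₀. The chance that any true null falls below that is at most m₀ × 0.05/m₀ = 0.05, whatever the dependence.
- *Thresholds.* m = 4: 0.0125, 0.0167, 0.025, 0.05, against 0.0125 throughout. m = 2: 0.025, 0.05, against 0.025. m = 1: 0.05 for both, so the methods coincide.

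**3. Ceiling on the gain.** Take a comparison with 80% power at an unadjusted two-sided 0.05 (normal approximation). Its power at 0.05/m is Φ(1.960 + 0.842 − z), where z is the upper 0.05/(2m) point.

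| m | z | Power at 0.05/m | Largest possible gain |
|---|---|---|---|
| 1 | 1.960 | 80.0% | 0 |
| 2 | 2.241 | 71.2% | 8.8 points |
| 4 | 2.498 | 61.9% | 18.1 points |
| 6 | 2.638 | 56.5% | 23.5 points |

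The ceiling is reached only if every other hypothesis in the family is rejected first.

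**4. Illustration by simulation.** From the documents: 42/45 and 18/30 subjects, 5% level. Assumed: two-sided tests; FMD SD 3 percentage points; within-subject correlation 0.5; means (placebo/antioxidant) young 8/8, older 5/6.5. Paired t tests within age, two-sample t tests between ages, both adjustments applied to the same P values, 20,000 runs. Repeat runs differ by about a point.

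| Subjects | Family | Comparison | Bonferroni | Holm | Gain |
|---|---|---|---|---|---|
| 42/45 | four | antioxidant vs placebo, older | 77% | 83% | 6 |
| 42/45 | four | young vs older on antioxidant | 42% | 51% | 9 |
| 42/45 | two (within age) | antioxidant vs placebo, older | 84.4% | 84.5% | about 0 |
| 42/45 | two (within visit) | young vs older on antioxidant | 51–52% | 63–64% | about 12 |
| 18/30 | four | antioxidant vs placebo, older | 53% | 58% | 5 |
| 18/30 | four | young vs older on antioxidant | 19% | 25% | 6 |

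In the family of four at 42/45, the chance of finding all three true differences rises from about 28% to 41%. The error on the one true null (antioxidant vs placebo in young) rises from about 1.3% to 3.4%, below 5%. Holm rejected everything that Bonferroni rejected in every run, and the chance of at least one rejection was identical.

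**5. Sensitivity.** If antioxidant closes the age gap (older 6.5/8), the gain for the older antioxidant effect in the family of four falls to about 1 point (76.2% to 77.3%). Over a wider grid (effects of 0 to 1.5 SD, families of two, four and six), gains ran from 0 to about 11 points at 42/45 and 0 to about 13 at 18/30.

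**The case against.** **Bonferroni is not wrong.** It controls the error rate, and nothing in the documents is contradictory on this point. This stands: the issue is efficiency only.

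**The family may hold one comparison.** Each factor has two levels, so a main effect is already a single contrast. If post-hoc testing is confined to it, m = 1 and nothing is lost. This also stands as a possibility. Naming a Bonferroni test has a purpose only if several cell-mean comparisons are meant, but the documents do not say so.

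**The powers are not the plan's powers.** Post-hoc tests open only after a significant main effect, and the table ignores that. In the assumed scenario the condition main effect is significant in about 63% of runs at 42/45 and 37% at 18/30. If it must open the antioxidant comparisons, neither 77% nor 83% is attainable. The undefined family and this condition are larger gaps than the choice between Bonferroni and Holm. The dominance result is unaffected, because both methods sit behind the same condition.

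**Stronger readings that a reader might infer.**

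- *That the trial loses a known amount, such as 3 to 9 points.* The documents give no family, effect size, SD or correlation, and the gain can be zero.
- *That the loss is worst in the 18/30 assay subset.* Under the same assumptions the gains there are 5 and 6 points, against 6 and 9 at 42/45. The subset concerns blood assays, for which no effect size or SD is given; the table merely reuses the FMD assumptions.
- *That these are the trial's key comparisons.* No comparison is designated as such.

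**Conclusion.** The plan's adjustment is valid but needlessly conservative for any family of more than one comparison. That Holm is at least as powerful, at the same 5% family-wise limit and without added assumptions, is a mathematical fact and does not depend on this trial's inputs.

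The size of the gain does depend on inputs that the documents omit. It is 0 for a family of one and close to 0 if only one difference in the family is real. It is about 0 to 12 points per comparison in families of two or four under the assumed means, SD and correlation with 42/45 subjects, before the main-effect condition. These are illustrations, not estimates of what this trial loses. The reading as single-step is the ordinary one but is not spelled out. Cheap improvement.

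**What to change.** In the Statistics paragraph, replace the Bonferroni test by *Holm's step-down Bonferroni procedure*, and report Holm-adjusted P values beside unadjusted confidence intervals. With four comparisons, test the ordered P values at 0.0125, 0.0167, 0.025 and 0.05, stopping at the first failure.

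The cost is one phrase; the raw P values are unchanged and no new data are needed. The downside is that simultaneous confidence intervals matching Holm are less simple than Bonferroni intervals, so the unadjusted intervals must be labelled as such.

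The document describes the conduct and analysis in the past tense. If results are already known, disclose the change as post hoc and show the Bonferroni results alongside, since this moves to a less strict adjustment after the data have been seen.
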